## **4 Analysis Populations**

### **4.1 Enrolled Population**

The enrolled population includes all patients who have passed screening and are enrolled into the study.

### **4.2 Safety Population**

The Safety Population includes all enrolled patients who received at least one injection of G100 after standard local radiation. Safety data analyses will be conducted on all patients in the Safety Population according to the treatment received.

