5.4 Primary Endpoint

- Part 1: The nature, frequency and severity of AEs and laboratory abnormalities up through Study Day 28 in patients with low-grade NHL receiving intratumoral G100 and local radiation
- Part 2: The nature, frequency and severity of AEs and laboratory abnormalities occurring in patients with follicular NHL receiving local radiation and either intratumoral G100 alone or sequential intratumoral G100 and anti-PD-1 therapy
- Part 3: The nature, frequency, and severity of AEs and laboratory abnormalities occurring in patients with follicular NHL receiving local radiation and G100 at 20 µg/dose
- Part 4: The nature, frequency and severity of AEs and laboratory abnormalities and the frequency of clinical responses occurring in patients with follicular NHL receiving intratumoral G100 at 20 µg/lesion in single or multiple tumor masses and pembrolizumab therapy
- Part 5: The nature, frequency and severity of AEs and laboratory abnormalities and the frequency of clinical responses occurring in patients with follicular NHL receiving rituximab therapy in combination with escalating doses of intratumoral G100 in single tumor lesions

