7.1 Inclusion Criteria

In order to be enrolled in the study, patients must meet **all** of the following inclusion criteria:

- 1) Follicular low-grade NHL (grades 1, 2, 3A): either treatment naïve or relapsed or refractory following at least one prior treatment. For France, patients with either relapsed or refractory only. In Part 1 Dose Escalation only, in addition to follicular NHL, marginal zone B cell lymphomas: either treatment naïve or relapsed or refractory following at least one prior treatment.
 - In Part 4, enrollment is limited to relapsed or refractory follicular NHL patients who have received at least 3 prior systemic treatments, one of which was or included an anti-CD20 antibody.
 - In Part 5, enrollment will include relapsed or refractory CD20+ follicular NHL following at least one but not more than 2 prior treatments.
- 2) Tumor mass(es) accessible for intratumoral injection and are being considered for local radiation therapy and at least one additional site of disease outside the radiation field for assessment of distal (abscopal) response. (Imaging assisted injections are allowed following approval by Medical Monitor)
 - For Parts 4 and 5, radiation therapy is omitted. Measurable tumor mass(es) accessible for intratumoral injection must be present for treatment and assessment of response.
- 3) ≥ 18 years of age
- 4) Life expectancy of ≥ 6 months per the investigator
- 5) Eastern Cooperative Oncology Group (ECOG) performance status of 0 or 1
- 6) ECG without evidence of clinically significant arrhythmia or ischemia
- 7) If female of childbearing potential (FCBP), willing to undergo pregnancy testing and agrees to use two methods of birth control or is considered highly unlikely to conceive during the dosing period and for three months after last study treatment, or if receiving pembrolizumab, four months after last treatment (See [Section 8.1.9](#) and [Appendix F: References for details](#))
- 8) If male and sexually active with a FCBP, must agree to use effective contraception such as latex condom or is sterile (e.g., following a surgical procedure) during the dosing period and for three months after last study treatment, or if receiving pembrolizumab, four months after last treatment (See [Section 8.1.9](#) and [Appendix F: References for details](#))

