8.3 Radiation

Patients will receive local palliative radiation to their tumor masses as part of normal cancer care. For this study, a standard short 2-day course of therapy of 2Gy qd \times 2 is recommended as the optimal dose to allow G100 treatment to begin shortly after starting radiation and to minimize any immune suppressive effects from the treatment. Other details and planning are at the discretion of the radiation therapist. Modifications to the dose should be discussed with Immune Design. Although steroids are sometimes used for radiation treatment related effects, use of concomitant or prophylactic steroids are not allowed on this study due to their potential immunosuppressive effects.

As part of this study, the injected lesion is followed for local effect, and untreated, abscopal lesions are followed for systemic treatment effect. Therefore the G100 treated / irradiated lesion should be one of the Index (target) lesions followed for response. In addition, the radiation treatment field should be reviewed by the radiation therapist to confirm the identity of all irradiated lesions and untreated “abscopal” lesions to be used to follow treatment response.

Patients in Parts 4 and 5 will not receive radiation.

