## 2 Study Objectives

### 2.1 Primary Objective

- In Part 1: Evaluate the safety and tolerability of ascending doses of intratumoral G100 in patients with low-grade non-Hodgkin's lymphoma (NHL) receiving local radiation
- In Part 2: Assess the safety and tolerability of intratumoral G100 or sequential intratumoral G100 and anti-programmed cell death protein 1 (PD-1) therapy in patients with follicular NHL receiving local radiation
- In Part 3: Evaluate the safety and tolerability of 20 µg/dose of intratumoral G100 in patients with low-grade NHL receiving local radiation
- In Part 4: Evaluate safety and preliminary clinical efficacy of intratumoral G100 at 20µg/lesion in single or multiple tumor lesions and pembrolizumab (anti-PD-1) therapy in patients with relapsed or refractory follicular NHL who have received at least 3 prior systemic treatments, one of which was or included an anti-CD20 antibody
- In Part 5: Evaluate safety and preliminary clinical efficacy of standard induction therapy with rituximab (anti-CD20) in combination with escalating doses of intratumoral G100 in single tumor lesions in patients with follicular NHL who have received at least one or two prior treatment(s)

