Treatment will follow a similar dose regimen as in "Part 2, Patient Expansion With or Without Pembrolizumab" group, except that radiation therapy has been omitted. G100 will be injected intratumorally beginning on Day 0, a second dose will be administered 5-7 days later (Study Day 5-7) and then dosing will continue weekly for up to 4 additional doses (6 total) as long as the tumor remains of sufficient size for injection. At least 1 lesion will be targeted to receive each dose of G100. If the lesion regresses, another lesion will be chosen for treatment (as described in the protocol). If the patient is entered in a cohort where more than one lesion is injected (cohorts 2 to 4), as many easily accessible tumors will be targeted and treated as specified for the cohort. Imaging assisted injections are allowed but the feasibility and safety of these treatments must be discussed first and approved by the Medical Monitor. If the tumor mass has not regressed completely from baseline, dosing may continue for 3 additional weekly intratumoral doses (9 total). On Day 14, pembrolizumab treatment will be initiated at a standard dose of 200 mg intravenously (IV) and then be administered every 3 weeks (q3W) IV for up to 2 years or until disease progression or unacceptable toxicity.

*Part 4 Dose Escalation:* In the Dose Escalation portion, safety will be assessed using a 3+3 design where 12 to 24 patients will be assigned to sequential cohorts of escalating number of G100 injected lesions in combination with standard dose pembrolizumab ([Figure 6](#)). Four cohorts are planned:

- Cohort 1: G100 20 µg/lesion in 1 tumor
- Cohort 2: G100 20 µg/lesion in 2 tumor lesions (40 µg total)
- Cohort 3: G100 20 µg/lesion in 3 tumor lesions (60 µg total)
- Cohort 4: G100 20 µg/lesion in 4 tumor lesions (80 µg total)

Once a Cohort dose level is established to be safe, patients who do not meet the criteria of sufficient numbers of injectable tumors to enter the next dose Cohort will be enrolled in a Patient Expansion group at a systemic dose level that has already been established as safe.

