Data from the G142 study indicate that the G100 intratumoral dose of 20 $\mu$ g is relatively safe with only grade 1 or 2 related AEs reported and no DLTs and that this higher dose appears to induce greater numbers of infiltrating CD8 T cells into the tumor. Recent preclinical data indicate that G100 doses greater than 20  $\mu$ g can lead to improved survival of animals in tumor models, further supporting that additional dose exploration may be warranted. Therefore, this arm will examine escalating doses of G100 plus rituximab in a single tumor site utilizing a 3+3 design in order to establish safety and examine clinical and biomarker responses. Once the highest safe dose/systemic exposure is determined from the Dose Escalation portion of the study, all safety, efficacy and biomarker data will be reviewed by the Sponsor (in collaboration with the independent DMC) and either the highest dose determined to be safe or the most biologically active and safe dose (if different than the MTD) will be chosen for further investigation. A Patient Expansion group would then begin. Details of Dose Escalation and Patient Expansion are described below.

*Part 5, Dose Escalation:* In the Dose Escalation portion, safety and efficacy of G100 injected into a single tumor lesion without radiation will be assessed using a 3+3 design where patients will be assigned to sequential cohorts of escalating doses of intratumoral G100 in combination with standard dose induction therapy with rituximab (Figure 8 and Figure 9). Treatment will begin on Day 0 with rituximab 375 mg/m^2 IV and continue weekly for a total of 4 doses. If there are no DLTs or significant safety events after the first dose of rituximab, G100 will be injected intratumorally beginning on Day 1, and then dosing will continue weekly for 3 additional doses (4 total) on a visit schedule that coincides with rituximab treatments as long as the tumor remains of sufficient size for injection. One lesion will be targeted to receive each dose of G100. If the lesion regresses, another lesion will be chosen for treatment. Imaging assisted injections are allowed but the feasibility and safety of these treatments must be discussed first and approved by the Medical Monitor. If the tumor lesion has not regressed completely after the first 4 doses of G100, dosing may continue for 2 additional weekly intratumoral doses (6 total). Following restaging, the patient may be eligible for a second course of G100.

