## **5.7 Safety Evaluation**

Safety evaluation will be based on safety population.

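### SAP 4.2 makes local radiation a condition of the Safety Population, so read as written no Part 4 or Part 5 patient enters the safety summaries

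*SAP*

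**What the plan says.** SAP 4.2 sets the rule: "The Safety Population includes all enrolled patients who received at least one injection of G100 after standard local radiation". It has no exception by part. SAP 5.7 then states "Safety evaluation will be based on safety population".

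On radiation in Parts 4 and 5, both documents are clear:

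- Protocol 7.1, inclusion criterion 2: "For Parts 4 and 5, radiation therapy is omitted".
- Protocol 8.3: "Patients in Parts 4 and 5 will not receive radiation".
- SAP 3.1, Part 4, which otherwise follows the Part 2 pembrolizumab regimen: "except that radiation therapy has been omitted".
- SAP 3.1, Part 5 Dose Escalation: "G100 injected into a single tumor lesion without radiation will be assessed using a 3+3 design".

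Safety is primary in both parts. Protocol 5.4 gives the Part 4 primary endpoint as "Part 4: The nature, frequency and severity of AEs and laboratory abnormalities and the frequency of clinical responses", with parallel wording for Part 5. SAP 2.1 carries the objectives over, for example "In Part 5: Evaluate safety and preliminary clinical efficacy of standard induction therapy with rituximab". The SAP version log shows that the final SAP was written for protocol version 04B and covers cohorts 1 to 5.

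**The concern.** The definition requires a treatment that two of the five parts do not give. A patient in Part 4 or 5 who receives a full course of G100 does not meet SAP 4.2.

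The Safety Population supports more than the adverse event tables. It is the basis for everything in SAP 5.7 (exposure, TEAEs, DLTs, laboratory values, vital signs) and for the deviation table in 5.4. It is one of two bases for the baseline, cancer-history and prior-therapy tables in 5.5, and it is used for the supportive efficacy analysis in 5.6. The medical-history listing in 5.5.3 is also tied to it.

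A programmer who follows 4.2 leaves two parts out of the summaries of their primary safety endpoint. One who ignores the clause departs from the signed SAP and gets a different denominator. An analysis-set definition should not leave that to the reader.

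**Working it through.** The plan gives no figure to reproduce here. The check compares the rule with the design, the rest of the SAP and the protocol.

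**Step 1: apply the rule.** Membership needs (a) at least one G100 injection and (b) that the injection followed standard local radiation. Write n4 and n5 for the G100-treated patients in Parts 4 and 5. Planned radiation in both parts is zero, so condition (b) fails for everyone:

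- Part 4: 0 of n4 qualify.
- Part 5: 0 of n5 qualify.

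This holds for any n4 and n5, so 100% of each part is excluded. With (b) removed, n4 of n4 and n5 of n5 qualify.

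**Step 2: see whether the SAP corrects itself.** It does not, but other sections show that exclusion was not intended:

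| SAP section | What it implies |
|---|---|
| 4.3 Efficacy Evaluable Population | Needs one G100 injection, with no radiation condition |
| 5.6.8 Immune response and biomarkers | Needs one G100 injection and available data, with no radiation condition |
| 5.7.1 Treatment exposure | Restricts radiation-dose counts to Parts 1 to 3 |
| 5.7.4 Laboratory evaluation | Schedules Part 4 thyroid tests |
| 9 Changes from protocol | Declares no narrowing of the safety set |

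Sections 4.2 and 4.3 together give an odd result: a Part 4 patient can be in the main efficacy analysis but outside the Safety Population, so the supportive efficacy analysis for that part would be empty while the main one is not.

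**Step 3: compare with the protocol.** It states the safety set in two ways, and neither mentions radiation:

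- Synopsis (Safety Monitoring) and 4.7: patients given one or more injections or doses of G100.
- 12.0 and 14.3.1: patients given at least one injection or undergoing a study-related procedure.

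**Step 4: find what is unaffected.** These do not use the Safety Population:

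- disposition (SAP 5.3, all enrolled patients);
- the main tumour-response analysis (4.3);
- the 3+3 decisions, which have their own evaluability rule in 3.1;
- DMC review (protocol 12.9, SAP 6);
- the general CRF listings (5.1) and the adverse event listings (5.7.2).

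The medical-history listing is the exception. Section 5.5.3 ties it to the Safety Population, while 5.1 promises listings of nearly all CRF data.

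**Step 5: size.** The documents give planned targets (22 efficacy evaluable patients in Part 4; 12 to 24 in escalation and 20 efficacy evaluable in expansion in Part 5). These are not counts of treated patients. SAP 3.1 replaces non-evaluable escalation patients, and SAP section 9 says that the sponsor terminated the study. I therefore give no share of the trial. The SAP lists no rituximab exposure summary and no rituximab-related adverse event table. That may mean Part 5 contributed few or no patients, or it may be a separate omission; the documents do not settle it.

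**The case against.** The strongest reply is that the intention is obvious. The clause suits Parts 1 to 3, other SAP sections treat radiation as belonging only to those parts, and the protocol gives a plain G100-based rule. An empty column would be noticed at the first table run. SAP section 1 allows deviations that are justified and documented in the study report. Safety is descriptive, so no test goes wrong, and much of the output is untouched: the baseline, cancer-history and prior-therapy tables are also produced on the Efficacy Evaluable population. With the study terminated, the excluded group could be small, and for Part 5 it could be empty.

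Most of this is true and limits the harm. This is a wording error and not a hidden bias, and its practical effect cannot be sized. But an inferable intention does not repair a signed definition, and relying on the deviation route means documenting a departure to obtain the ordinary safety tables.

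A second objection also stands. Deleting the clause brings 4.2 into line with the synopsis and protocol 4.7, but leaves it narrower than protocol 12.0 and 14.3.1, which add patients who undergo a study-related procedure. The SAP should therefore state which protocol wording it follows.

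**Conclusion.** The concern holds. As written, SAP 4.2 contradicts the Part 4 and Part 5 design in both documents and excludes every patient in those parts from the summaries of a primary endpoint. That conclusion rests only on the text and on patients in these parts receiving no radiation, as planned. The consequence is missing or reader-dependent descriptive summaries, not a wrong test. The number of patients affected is unknown. It needs correcting because the error is complete for any part that treated patients.

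**What to change.** Delete the last four words of the first sentence of SAP 4.2, so that the Safety Population is all enrolled patients who received at least one injection of G100. This costs four words, needs no new data and matches the protocol synopsis and section 4.7.

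Add one sentence to SAP section 9 stating that this definition is used in preference to the broader wording of protocol 12.0 and 14.3.1.

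A separate, lesser point can be settled in the same entry. In Part 5, rituximab is given on Day 0 and G100 starts on Day 1 only if no DLT or significant safety event follows it (protocol 6.1). A patient who stops after rituximab alone is in the safety set under 12.0 and 14.3.1, but not under the synopsis, 4.7 or the amended 4.2. One solution is to include Part 5 patients who received any rituximab. If so, state that their treatment-emergent period starts at the first rituximab dose, and note that SAP 5.7.2 lists no rituximab-related table. I see no need to add patients from Parts 1 to 3 who had radiation but no G100; the entry should say that they are left out.

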### **4.3 Efficacy Evaluable Population**

The Efficacy Evaluable population includes all enrolled patients without major protocol deviations, who have received at least one injection of G100, and have had baseline and at least one post-baseline disease assessment.

The Efficacy Evaluable population will be used for the tumor response analysis based on irRC, including overall tumor response and time to disease progression (TTP).

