Following each safety evaluation by the DMC and the Sponsor, a further modification to the dose/treatment schedule could be recommended. For all treatment groups, the DMC and Sponsor will review all events meeting the criteria for DLTs and all SAEs considered at least possibly related to the study regimen as they are reported on an ongoing basis. In addition, the DMC and Sponsor will review all safety data for any trends at least once every 3 months. SAE reports considered at least possibly related to the study regimen and are unexpected will be expedited to regulatory authorities, investigators, and DMC members. In addition to the stopping rules (DLTs within the initial 28 days), these reviews may lead to modification or stopping of the treatment program if related, treatment-emergent AEs indicate a safety profile that is inconsistent or significantly worse than previously reported with the use of either G100 or pembrolizumab alone or rituximab alone.

All AEs and DLTs observed during dose escalation of any treatment arm and/or patient expansion meeting the criteria of a stopping rule will be reviewed by the DMC. If there is

disagreement between the DMC and the investigator's assessment regarding the relationship of the event to study agent or to the clinical relevance (e.g., lab abnormality), the Sponsor in consultation with the DMC may determine to stop the treatment or continue. In the later case, the AE may become a medical event of interest and be tracked closely for additional events occurring in future with IT G100

All patients treated with one or more injections of G100 will be considered part of the safety data set. Patients will be followed every 8 weeks until disease progression as defined by the irRC. Patients with disease progression by irRC (or symptomatic deterioration) will be followed thereafter every 8-12 weeks by telephone or clinical visit for up to one year (or longer if the patient agrees) after first study injection as long as they are able to engage in follow-up. Follow-up will ascertain vital status (survival status) as well as cancer status (e.g., lymphoma transformation), post-treatment anti-cancer therapy (including time to next treatment, treatment details, and clinical response), and any SAE that might be possibly related to G100 treatment.

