For this analysis, 22 efficacy evaluable patients will be required. Efficacy evaluable patients are patients who received at least 3 doses of G100 at 20 μ g/lesion and at least 1 dose of pembrolizumab, had at least one post baseline tumor assessment, and had no major protocol deviations that impact the efficacy of the study treatment or the assessment of response. Patients who received G100 20 μ g/lesion during Dose Escalation in Part 4 may be included in clinical response analysis. With a target ORR of 40%, if ≤ 5 responders are observed among 22 evaluable patients, we will conclude futility with 7.2% error rate. The Sponsor will use this analysis to decide whether to continue further development of this regimen. Early acceptance of treatment at the end of the 22 evaluable patients is not permitted. If the true ORR for this group is 20% and 20% ORR is considered not clinically meaningful, the probability of observing $\leq 5/22$ responders and stopping the study is 73.3%.

In Part 5, G100 Plus rituximab, after Dose Escalation has been completed, patients will be treated with intratumoral G100 at the recommended dose level in combination with rituximab. The purpose of this Patient Expansion group will be to explore the safety and clinical outcome of patients treated at a biologically active and safe G100 dose level administered into single tumor lesion in combination with rituximab. This analysis is designed to be exploratory and will evaluate safety, clinical outcome and exploratory biomarkers.

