An exploratory analysis will be performed on 20 efficacy evaluable relapsed or refractory FL patients and will include analyses of the frequency and duration of CRs. Efficacy evaluable patients are patients who received at least 3 injections of G100 at the recommended dose and 3 doses of rituximab, had at least one post baseline tumor assessment, and had no major protocol deviations that impact the efficacy of the study treatment or the assessment of response. Five or more CRs in 20 patients treated with G100 plus rituximab will signal an improvement of CR rate over 10%. For reference, the probability of observing ≤ 4 CRs in 20 patients is 5.1% if the true CR rate is 40% (the targeted CR rate). Patients who received G100 at the recommended dose during Dose Escalation in Part 5 may be included in clinical response analysis. With 20 efficacy evaluable patients, and a historical CR rate of 10%, assuming a true CR rate of 32% in the G100 plus rituximab, this subgroup analysis has 82% power to detect a signal of an improvement in CR from 10% at a 1-sided alpha of 0.05.

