In Part 4, G100 Plus Pembrolizumab, at least 22 evaluable patients will be enrolled and treated as part of a Dose Escalation group or a Patient Expansion group with intratumoral G100 in combination with pembrolizumab. The purpose of this treatment regimen will be to explore the safety and preliminary clinical efficacy and biomarker changes of patients treated with G100 at a dose of 20 µg/lesion injected in single or multiple lesions. The administered dose of G100 will depend on the number of potentially injectable lesions and whether the MTD has been established during Dose Escalation. One or more lesions will be targeted for injection and each lesion would receive 20µg of G100 intratumorally (or 10 µg G100 if 20 µg/lesion in a single lesion is not tolerated) as long as the total number of treated tumor lesions and total systemic dose does not exceed the MTD (if established) or 80 µg total dose (20 µg injected in 4 lesions). This analysis is designed to be exploratory and will evaluate safety, clinical outcome and exploratory biomarkers to guide further clinical development. Clinical efficacy including ORR and DOR will be evaluated in relapsed or refractory FL patients who received  $\geq 3$  prior systemic therapies.

For this analysis, 22 efficacy evaluable patients will be required. Efficacy evaluable patients are patients who received at least 3 doses of G100 at 20 µg/lesion and at least 1 dose of pembrolizumab, had at least one post baseline tumor assessment, and had no major protocol deviations that impact the efficacy of the study treatment or the assessment of response. Patients who received G100 20µg/lesion during Dose Escalation in Part 4 may be included in clinical response analysis. With a target ORR of 40%, if  $\leq 5$  responders are observed among 22 evaluable patients, we will conclude futility with 7.2% error rate. The Sponsor will use this analysis to decide whether to continue further development of this regimen. Early acceptance of treatment at the end of the 22 evaluable patients is not permitted. If the true ORR for this

group is 20% and 20% ORR is considered not clinically meaningful, the probability of observing  $\leq 5/22$  responders and stopping the study is 73.3%.

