In Part 5, G100 Plus rituximab, after Dose Escalation has been completed, patients will be treated with intratumoral G100 at the recommended dose level in combination with rituximab. The purpose of this Patient Expansion group will be to explore the safety and clinical outcome of patients treated at a biologically active and safe G100 dose level administered into single tumor lesion in combination with rituximab. This analysis is designed to be exploratory and will evaluate safety, clinical outcome and exploratory biomarkers.

An exploratory analysis will be performed on 20 efficacy evaluable relapsed or refractory FL patients and will include analyses of the frequency and duration of CRs. Efficacy evaluable patients are patients who received at least 3 injections of G100 at the recommended dose and 3 doses of rituximab, had at least one post baseline tumor assessment, and had no major protocol deviations that impact the efficacy of the study treatment or the assessment of response. Five or more CRs in 20 patients treated with G100 plus rituximab will signal an improvement of CR rate over 10%. For reference, the probability of observing  $\leq 4$  CRs in 20 patients is 5.1% if the true CR rate is 40% (the targeted CR rate). Patients who received G100 at the recommended dose during Dose Escalation in Part 5 may be included in clinical response analysis. With 20 efficacy evaluable patients, and a historical CR rate of 10%, assuming a true CR rate of 32% in the G100 plus rituximab, this subgroup analysis has 82% power to detect a signal of an improvement in CR from 10% at a 1-sided alpha of 0.05.

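### SAP 4.2 makes radiation a condition of the Safety Population although Parts 4 and 5 give none, and SAP 4.3 and 3.4 use the name Efficacy Evaluable for two different sets

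*SAP*

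**What the plan says.** **Safety Population.** SAP 4.2 requires "at least one injection of G100 after standard local radiation". SAP 5.7 bases the whole safety evaluation on this set, and SAP 5.6 uses it for the supportive efficacy analysis. Protocol 8.3 states: "Patients in Parts 4 and 5 will not receive radiation". The design text in SAP 3.1 agrees for both parts. Protocol 4.7 has no radiation condition: "All patients treated with one or more injections of G100 will be considered part of the safety data set". Nor does protocol 14.3.1, which asks for one injection of study drug or a study-related procedure.

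**Efficacy Evaluable, SAP 4.3.** One definition covers all parts. It takes those "who have received at least one injection of G100, and have had baseline and at least one post-baseline disease assessment", and it leaves out anyone with a major deviation. It is assigned to the irRC response and time-to-progression analyses. SAP 5.6 makes it the main efficacy set.

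**Efficacy Evaluable, SAP 3.4 and protocol 14.2.** For Part 4: "Efficacy evaluable patients are patients who received at least 3 doses of G100" at 20 µg/lesion, with at least one dose of pembrolizumab. For Part 5: "Efficacy evaluable patients are patients who received at least 3 injections of G100 at the recommended dose and 3 doses of rituximab". In both parts the patient must also have "had at least one post baseline tumor assessment" and no major deviation that affects efficacy or the assessment of response. The rules follow in the same paragraphs. Part 4 is futile at 5 or fewer responders among 22. For Part 5, "Five or more CRs in 20 patients treated with G100 plus rituximab will signal an improvement of CR rate over 10" per cent.

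**The concern.** Safety is a primary endpoint in Parts 4 and 5, and so is the frequency of clinical response (protocol 5.4). A population definition is an operative instruction: datasets are programmed from it. Followed to the letter, SAP 4.2 leaves the Safety Population empty for two of the five parts.

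The shared name raises a different question. A reader of the final tables will see an overall response rate (ORR) or complete response (CR) rate labelled Efficacy Evaluable and will naturally set it against the 22-patient or 20-patient rule. Under SAP 4.3 and 5.6 that rate may be computed on other patients than those the rule counts. SAP 9, which lists changes from the protocol's planned analysis, mentions only the Lugano criteria and independent radiology review, so neither difference is declared.

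**Working it through.** **1. The plan's own figures.** Inputs are from SAP 3.4 and protocol 14.2; X is the number of responders (Part 4) or CRs (Part 5), exact binomial.

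- Part 4, n = 22, ORR 40%: P(X ≤ 5) = 0.0722; stated 7.2%.
- Part 4, n = 22, ORR 20%: P(X ≤ 5) = 0.7326; stated 73.3%.
- Part 5, n = 20, CR rate 32%: P(X ≥ 5) = 0.8173; stated 82%.
- Part 5, n = 20, CR rate 10%: P(X ≥ 5) = 0.0432, inside the one-sided 0.05.
- Part 5, n = 20, CR rate 40%: P(X ≤ 4) = 0.0510; stated 5.1%.

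All reproduce. They belong to the sets defined in 3.4/14.2 and need no change.

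**2. Safety Population.** SAP 4.2 requires prior radiation. Protocol 8.3 and SAP 3.1 give none in Parts 4 and 5. The number of Part 4/5 patients meeting 4.2 as written is therefore zero. This was not the intention: SAP 5.7.1 limits the count of radiation doses to Parts 1 to 3, and SAP 5.7.4 lists Part 4 thyroid visits.

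**3. The two Efficacy Evaluable sets.**

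| Requirement | SAP 4.3 | SAP 3.4 / protocol 14.2 |
|---|---|---|
| G100 | 1 injection, any dose | at least 3, at 20 µg/lesion (Part 4) or the recommended dose (Part 5) |
| Partner drug | none | at least 1 pembrolizumab (Part 4); 3 rituximab (Part 5) |
| Post-baseline assessment | at least 1 | at least 1 |
| Major deviations | any excludes | only those affecting efficacy or response assessment |

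SAP 4.3 is looser on exposure and, as worded, stricter on deviations. Neither set contains the other. SAP 5.4 leaves the choice of excluding deviations to the study team, which may narrow that second gap.

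**4. Who can fall between them.** In Part 4, pembrolizumab starts on Day 14, the day of the third G100 dose. An assessed patient who stops after one or two injections can enter the 4.3 set without having had the combination. Part 5 escalation patients at a dose other than the recommended one meet 4.3 but not 3.4, although SAP 5.6 also reports by treatment, which may separate them. Protocol 10.3.18 (Part 4) and 10.3.25 (Part 5) allow remaining G100 treatments to be cancelled when the injected tumor has regressed and no injectable lesion remains. A patient with fewer than 3 doses may therefore be an early responder.

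**5. Effect on a reported rate.** The counts below are assumptions; the documents give none.

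- Part 4: 6/22 = 27.3% (exact 95% CI 10.7 to 50.2%). One extra under-exposed patient gives 6/23 = 26.1% if a non-responder and 7/23 = 30.4% if a responder. Two give 6/24 = 25.0% to 8/24 = 33.3%.
- Part 5: 5/20 = 25.0%. One extra gives 5/21 = 23.8% or 6/21 = 28.6%. Two give 5/22 = 22.7% to 7/22 = 31.8%.
- Dropping one Part 4 patient for a major deviation unrelated to efficacy gives 6/21 = 28.6% or 5/21 = 23.8%.

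**The case against.** The strongest reply is that the decision rules are not ambiguous. SAP 3.4 and protocol 14.2 state each rule beside its own evaluable definition, and no section counts either rule on the 4.3 set. This stands. A reader might infer that the false-futility rate or the power has been degraded. The documents do not support that, because it would require the 22 or 20 to be counted by SAP 4.3, which the plan nowhere says. What remains is one name shared by a rule set and a reporting set.

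A reader might also infer that the looser exposure threshold lowers the reported rate. That assumes every under-exposed patient is a non-responder, and the cancellation provisions after regression contradict it.

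A third tempting inference is that patients with no post-baseline assessment are not handled anywhere. SAP 5.6.2 counts as responders only patients with a best response of irCR or irPR, so an unassessed patient is a non-responder in the Safety-population ORR. The progression-free survival rules in SAP 5.6.4 and Table 7 also work in that analysis once 4.2 is corrected.

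Finally, the radiation phrase is plainly carry-over wording and the protocol already has the right safety set. That limits the practical risk. It does not make the SAP definition right, nor does it remove the conflict with protocol 4.7 and 14.3.1.

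**Conclusion.** Both definitions need correcting as written; severity is minor. Applied literally, SAP 4.2 removes every Part 4 and Part 5 patient from the safety analyses and the supportive efficacy analysis. SAP 4.3 and SAP 3.4/protocol 14.2 give one name to two sets that are not nested, so a reported Part 4 ORR or Part 5 CR rate may not be the rate its rule refers to.

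Neither the direction nor the size of the discrepancy can be stated. With one or two assumed extra patients, the illustrated Part 4 rate stays between 25.0% and 33.3%, well inside the interval of 10.7 to 50.2% around 6/22. The plan's operating characteristics are unaffected. The analyses are exploratory (protocol 14.1, SAP 8), and SAP 9 records that the sponsor terminated the study. The corrections settle what the reported figures mean; they do not show that any result is biased.

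**What to change.** 1. In SAP 4.2, delete the radiation condition or confine it to Parts 1 to 3, so that the set agrees with protocol 4.7 and 8.3.
2. In SAP 4.3, give the SAP 3.4/protocol 14.2 set its own name, for example Part 4/5 decision-rule evaluable. State that the two rules, and the Part 4 ORR and Part 5 CR rates tied to them, use it.
3. Keep the broader 4.3 set for by-part and overall reporting. Replacing it with part-specific criteria would make the overall row mix different exposure requirements.

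The cost is a few sentences, with no new data and no change to the protocol's rules. The downside is one extra denominator shown for Parts 4 and 5.
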